13.3 Pembrolizumab

(Refer to FDA-approved package insert for complete product information)

13.3.1 Description:

Pembrolizumab is a humanized monoclonal IgG4 antibody directed against the human cell surface receptor, programmed death-1, (PD-1). Following administration, pembrolizumab binds to PD-1 and blocks the interaction between PD-1 and its ligands.

13.3.2 How Supplied:

Keytruda (pembrolizumab) will be purchased by the NIH Clinical Center Pharmacy Department from commercial sources. Pembrolizumab is supplied in a single-use 50 mg vial as pembrolizumab lyophilized powder and as a single use 25 mg/mL ready-to-use solution containing 4 mL (100 mg/vial).

13.3.3 Reconstitution/Dose Preparation:

The lyophilized powder is reconstituted with 2.3 mL Sterile Water for injection, USP, and the resultant concentration is 25 mg/mL. Diluent should be directed against the side of the vial to avoid excess foaming. Swirl contents gently until completely dissolved. Let contents sit for up to 5 minutes to allow all bubbles to clear. Do not shake.

The ready-to-use solution or reconstituted lyophilized powder must be further diluted prior to administration. It may be diluted in 0.9% Sodium Chloride injection, USP or 5% Dextrose Injection, USP. The final concentration of the dilution solution should be between 1 mg/ml to 10 mg/ml.

13.3.4 Stability/Storage:

The reconstituted lyophilized power is stable for up to 6 hours at room temperature or up to 24 hours at when stored under refrigeration (2-8°C or 36-46°F).

The diluted solution is stable for up to 6 hours at room temperature or up to 24 hours at when stored under refrigeration (2-8°C or 36-46°F).

13.3.5 Administration:

Pembrolizumab will be given at a fixed dose of 200 mg as an intravenous infusion over 30 minutes through an intravenous line containing a sterile, non-pyrogenic, low-protein binding 0.2 micron to 5 micron in-line or add-on filter.

13.3.6 Toxicities:

This protocol uses commercial supply of pembrolizumab; please refer to current FDA-approved package insert.

15 APPENDICES AND SUPPLEMENTARY TABLES

15.1 SUPPLEMENTARY TABLES

15.1.1 Supplementary Table 1: Cancer/Testis Genes and Their Chromosomal Locations (Partial List)

Gene family	Family members	CT identifier	Chromosomal localization
MAGEA	MAGEA1, MAGEA2, MAGEA3, MAGEA4, MAGEA5, MAGEA6, MAGEA8, MAGEA9, MAGEA10, MAGEA11, MAGEA12	CT1	Xq28
BAGE	BAGE	CT2	21p11.1
MAGEB	MAGEB1, MAGEB2, MAGEB3, MAGEB4, MAGEB5, MAGEB6	CT3	Xp21.3
GAGE	GAGE1, GAGE2, GAGE3, GAGE4, GAGE5, GAGE6, GAGE7, GAGE8	CT4	Xp11.23
SSX	SSX1, SSX2, SSX3, SSX4	CT5	Xp11.23-p11.22.
NY-ESO-1	CTAG1B, CTAG2	CT6	Xq28
MAGEC1	MAGEC1	CT7	Xq26
SYCP1	SYCP1	CT8	1p12-p13
BRDT	BRDT	СТ9	1p22.1
MAGEC2	MAGEC2	CT10	Xq27
SPANX	SPANXA1, SPANXB1, SPANXC, SPANXD	CT11	Xq27.1
XAGE	XAGE1	CT12	Xp11.22
HAGE	DDX43	CT13	6q12-q13.
SAGE	SAGE1	CT14	Xq26.
ADAM2	ADAM2	CT15	8p11.2.
PAGE-5	PAGE5	CT16.1	Xp11.23
LIPI	LIPI	CT17	21q11.2
NA88A pseudogene	VENTXP1	CT18	Xp21.3.
IL13RA	IL13RA2	CT19	Xq13.1-q28
TSP50	TSP50	CT20	3p12-14
CTAGE-1	CTAGE1	CT21.1	18p11.2
SPA17	SPA17	CT22	11q24.2
ACRBP	ACRBP	CT23	12p12-p13.
CSAG	CSAG1, CSAG2	CT24	Xq28.
MMA1	DSCR8	CT25	21q22.2.
CAGE/DDX53	DDX53	CT26	Xp22.11
BORIS	CTCFL	CT27	20q13.31
HOM-TES-85	LUZP4	CT28	Xq23
AF15q14	CASC5	CT29	15q14
HCA661	TFDP3	CT30	Xq26.2
JARID1B	JARID1B	CT31	1q32.1.
LDHC	LDHC	CT32	11p15.3-p15.5

Gene family	Family members	CT identifier	Chromosomal localization
MORC	MORC1	CT33	3q13
SGY-1	DKKL1	CT34	19q13.33
SPO11	SPO11	CT35	20q13.2-q13.3
TPX1	CRISP2	CT36	6p21-qter
NY-SAR-35	FMR1NB	CT37	Xq27.3-q28.
FTHL17	FTHL17	CT38	Xp21
NXF2	NXF2	СТ39	Xq22.1
TAF7L	TAF7L	CT40	Xq22.1
TDRD1	TDRD1	CT41	10q25.3.
TEX15	TEX15	CT42	8p12
FATE	FATE1	CT43	Xq28
ТРТЕ	ТРТЕ	CT44	21p11
CT45	CT45-1, CT45-2, CT45-3, CT45-4, CT45-5, CT45-6	CT45	Xq26.3
HORMAD1	HORMAD1	CT46	1q21.2.
CT47	CT47-1, CT47-2, CT47-3, CT47-4, CT47-5, CT47-6, CT47-7, CT47-8, CT47-9, CT47-10, CT47-11, CT47-12	CT47	Xq24
SLCO6A1	SLCO6A1	CT48	5q21.1
TAG	TAG	CT49	Na
LEMD1	LEMD1	CT50	1q32.1
HSPB9	HSPB9	CT51	1p36.2-p35
CCDC110	CCDC110	CT52	4q35.1
ZNF165	ZNF165	CT53	6p21.3
SPACA3	SPACA3	CT54	17q11.2
CXorf48	CXorf48	CT55	Xq26.3
THEG	THEG	CT56	19pter-p13
ACTL8	ACTL8	CT57	1p36.2-p35
NLRP4	NLRP4	CT58	1p36.2-p35
COX6B2	COX6B2	CT59	19q13.42
LOC348120	LOC348120	CT60	15q11.2
CCDC33	CCDC33	CT61	15q24.1
LOC196993	LOC196993	CT62	15q23
PASD1	PASD1	CT63	Xq28
СТ64	CT64/BX103208	CT64	3q26.1.
TULP2	TULP2	CT65	19q13.1.
СТ66	CT66/AA884595	CT66	7q11.22.
KLKBL4	KLKBL4	CT67	16q21
RBM46	RBM46	CT68	4q32.1
СТ69	CT69/BC040308	CT69	6q23.2
СТ70	CT70/BI818097	CT70	Na

Gene family	Family members	CT identifier	Chromosomal localization
SPINLW1	SPINLW1	CT71	20q12-q13.2
TSSK6	TSSK6	CT72	19p13.11
ADAM29	ADAM29	CT73	4q34.
CCDC36	CCDC36	CT74	3p21.31
LOC440934	LOC440934	CT75	2q36.1
SYCE1	SYCE1	CT76	10q26.3
CPXCR1	CPXCR1	CT77	Xq21.3
TSPY1	TSPY1	CT78	Yp11.2
TSGA10	TSGA10	CT79	2q11.2.
PIWIL2	PIWIL2	CT80	8p21.3
ARMC3	ARMC3	CT81	10p12.31
AKAP3	AKAP3	CT82	12p13.3.
CXorf61	Cxorf61	CT83	Xq23
PBK	РВК	CT84	8p21.2
C21orf99	C21orf99	CT85	21q11.2
OIP5	OIP5	CT86	15q15.1
CEP290	CEP290	CT87	12q21.32
CABYR	CABYR	CT88	18q11.2
SPAG9	SPAG9	CT89	17q21.33.
MPHOSPH1	MPHOSPH1	СТ90	10q23.31
ROPN1	ROPN1	CT91	3q21.1.
PLAC1	PLAC1	СТ92	Xq26
CALR3	CALR3	СТ93	19p13.1
PRM	PRM1/PRM2	CT94.1	16p13.2
CAGE1	CAGE1	СТ95	6p24.3
СТ96	ТТК	СТ96	6q13-q21
LY6K	LY6K	СТ97	8q24.3
IMP-3	IMP-3	CT98	7p11.
AKAP4	AKAP4	СТ99	Xp11.2
DPPA2	DPPA2	CT100	3q13.13
KIAA0100/MLAA-22	KIAA0100	CT 101	7q11.2
TCC52	TCC52	CT102	9p13.3
SEMG1	SEMG1	CT103	20q12-q13.2
РОТЕ	POTE21, POTE2, POTE8, POTE14, POTE15, POTE18, POTE22	CT104	2q21.1
FLJ36144/MAD-CT2	MAD-CT2	CT105	15q11.2.
NUF2/CDCA1	CDCA1	CT106	1q23
RHOXF2/PEPP2	PEPP2	CT107	Xq24

Gene family	Family members	CT identifier	Chromosomal localization
ОТОА	ОТОА	CT108	16p12.2
CCDC62	CCDC62	CT109	12q24.31
GPATCH2	GPATCH2	CT110	1q41

Na: not available

CT Family						Frequ	ency (%	6) of Ex	pressio	n in Tur	nor Typ	e				
(Member)	Bla d	Brn	Brst	Col	Eso	Gas	H/N	Live r	Leu k/ Ly mp h	Lun g (NS CL C)	Mel	Ov	Pan cr	Pro s	Ren al	Sarc
MAGEA1/ CT1.1	22	-	18	2	53	29	28	80	0	49	48	28	-	15	0	14
BAGE1/C T2.1	15	-	10	0	-	-	8	-	0	4	26	15	-	0	0	6
MAGEB1/ CT3.1	0	0	17	0	-	0	0	-	0	14	22	-	-	0	0	9
GAGE/CT 4.1	12	-	9	0	-	-	19	38 ^b	1	19	28	31	-	10	0	25
SSX2/CT5 .2	44	6	7	12	-	-	35	9 ^b	36	16	35	-	-	40	5	50
NY-ESO- 1/CT6.1	80	0	30	0	-	0	-	29	0	17	34	25	0	25	9	0
MAGEC1/ CT7.1	44	-	30	10	-	-	36	-	-	33	70	-	-	-	-	60
SYCP1/C T8	-	47	20	0	-	7	-	28 ^b	0	7	14	0	-	0	8	0
BRDT/CT 9	0	-	0	0	8	-	8	-	-	25	0	-	-	-	0	-
MAGEE1/ CT10	44	-	38	0	-	-	36	-	-	24	50	-	-	-	-	0
SPANXC/ CT11.3	9	-	25	22	0	-	-	-	-	33	70	-	0	-	-	-
XAGE- 1a/CT12.1 a	-	-	-	-	-	-	-	-	-	-	8	-	-	-	-	22
HAGE/CT 13	24	37	5	31	27	-	-	20	9	32	17	-	-	22	6	20
SAGE/CT 14	12	0	5	0	20	-	17	-	4	22	4	-	-	0	5	5
ADAM2/ CT15	-	-	0	0	-	-	-	-	-	0	0	0	-	-	12	-
PAGE- 5/CT16	-	-	5	11	-	-	-	-	-	39	22	0	-	-	44	-
LIP1/CT1 7	-	-	5	0	-	-	-	-	-	0	0	0	-	-	25	-

15.1.2 Supplementary Table 2: Frequency of CT Gene Expression in Various Human Cancers as Determined by Semi-Quantitative RT-PCR

CT Family						Frequ	ency (%	6) of Ex	pressio	n in Tur	nor Typ	be				
(Member)	Bla d	Brn	Brst	Col	Eso	Gas	H/N	Live r	Leu k/ Ly mp h	Lun g (NS CL C)	Mel	Ov	Pan cr	Pro s	Ren al	Sarc
NA88/CT 18	-	-	-	-	-	-	-	-	-	-	11	-	-	-	-	-
TSP50/CT 20	-	-	28	-	-	-	-	-	-	-	-	-	-	-	-	-
CTAGE- 1/CT21.1	-	-	-	-	-	-	-	-	35	-	-	-	-	-	-	-
SPA17/CT 22	-	-	-	-	-	-	-	-	26	-	-	-	-	-	-	-
OYTES1/ CT23	28	-	40	15	-	0	-	40	-	20	-	-	-	-	0	-
MMA1a/C T25.1a	-	-	0	0	0	-	-	-	-	40	26	-	0	-	-	18
CAGE/CT 26	-	-	-	-	-	89	-	-	-	100	-	-	-	-	-	-
HOMTES 85/CT28	-	35	0	10	-	-	-	19	-	28	36	32	-	0	-	-
D40/CT29	-	20	-	13	-	0	-	-	-	41	-	36	27	-	-	-
HCA661/ CT30	0	-	-	-	-	0	0	29	-	-	20	-	-	-	-	-
PLU- 1/CT31	-	-	86	-	-	-	-	-	-	-	-	-	-	-	-	-
LDHC/CT 32	-	-	35	15	-	-	-	-	-	47	44	42	-	37	57	-
MORC/C T33	-	-	0	0	-	-	-	-	-	18	18	14	-	0	0	-
SGY- 1/CT34	-	-	20	0	-	-	-	-	-	12	25	57	-	12	0	-
SPO11/CT 35	-	-	0	0	-	-	-	-	-	0	6	0	-	0	0	-
TPX1/CT3 6	-	-	15	0	-	-	-	-	-	-	6	14	-	37	14	-
NYSAR35 /CT37	42	-	23	0	8	-	-	-	-	17	6	8	-	-	0	8
FTHL17/C T38	22	-	14	0	0	-	10	-	0	25	0	-	-	0	0	0
NXF2/CT 39	19	-	0	11	12	-	5	-	0	15	55	-	-	14	0	27

CT Family		Frequency (%) of Expression in Tumor Type														
(Member)	Bla d	Brn	Brst	Col	Eso	Gas	H/N	Live r	Leu k/ Ly mp h	Lun g (NS CL C)	Mel	Ov	Pan cr	Pro s	Ren al	Sarc
TAF7L/C T40	10	-	0	0	0	-	10	-	0	9	21	-	-	0	0	12
TDRD1/C T41.1	28	-	37	0	10	-	22	-	5	5	0	-	-	38	0	0
TEX15/C T42	21	-	0	0	20	-	11	-	0	21	27	-	-	12	33	28
FATE/CT 43	-	-	-	21	-	7	-	66	-	0	-	-	-	-	-	-
TPTE/CT4 4	-	-	-	0	-	0	-	39	-	36	-	-	-	-	-	-

^aAbbreviations: Blad, bladder; Brn, brain; Brst, breast; Col, colon; Gas, gastric; H/N, head and neck; Leuk, leukemia; Lymph, lymphoma, NSCLC, non-small cell lung carcinoma; Mel, melanoma; Ov, ovarian; Pancr, pancreatic; Pros, prostate; Sarc, sarcoma.

Reprinted from ref (126)

15.2 APPENDICES

15.2.1 Appendix 1: Performance Status Criteria

ECO	G Performance Status Scale	Ka	rnofsky Performance Scale
Grade	Descriptions	Percent	Description
	Normal activity. Fully active, able	100	Normal, no complaints, no evidence of disease.
0	to carry on all pre-disease performance without restriction.	90	Able to carry on normal activity; minor signs or symptoms of disease.
1	Symptoms, but ambulatory. Restricted in physically strenuous activity, but ambulatory and able	80	Normal activity with effort; some signs or symptoms of disease.
I	to carry out work of a light or sedentary nature (e.g., light housework, office work).	70	Cares for self, unable to carry on normal activity or to do active work.
2	In bed <50% of the time. Ambulatory and capable of all self-care, but unable to carry out	60	Requires occasional assistance, but is able to care for most of his/her needs.
	any work activities. Up and about more than 50% of waking hours.	50	Requires considerable assistance and frequent medical care.
3	In bed >50% of the time. Capable of only limited self-care, confined	40	Disabled, requires special care and assistance.
5	to bed or chair more than 50% of waking hours.	30	Severely disabled, hospitalization indicated. Death not imminent.
4	100% bedridden. Completely disabled. Cannot carry on any	20	Very sick, hospitalization indicated. Death not imminent.
т	self-care. Totally confined to bed or chair.	10	Moribund, fatal processes progressing rapidly.
5	Dead.	0	Dead.

		_		DATE	April 2015	
Sun	Mon	Tue	Wed	Thu	Fri	Sat
			1	2	3	4
-						
-						
5	(7	8	9	10	11
3	6	7	8	9	10	11
12	13	14	15	16	17	18
	·····					
10	•	0.1				
19	20	21	22	23	24	25
26	27	28	29	30		
-						
Take Medication	s: DAC and TH	U once per day o	n assigned days. T	HU should be tak	en approximatel	y 2 hours before
Take Medication	s: DAC and TH or 2 h	U once per day of ours after a meal Dates	n assigned days. T . DAC should be t Treated at Home	aken 1 hour after Treated in doctor's	en approximately THU. Hospitalized	y 2 hours before Comments
GI	s: DAC and TH or 2 h	ours after a meal	DAC should be t Treated at	aken 1 hour after	THU.	
GI diarrhea	s: DAC and TH or 2 h	ours after a meal	DAC should be t Treated at	aken 1 hour after Treated in doctor's	THU.	
GI diarrhea nausea	s: DAC and TH or 2 h	ours after a meal	DAC should be t Treated at	aken 1 hour after Treated in doctor's	THU.	
GI diarrhea nausea vomiting	s: DAC and TH or 2 h	ours after a meal	DAC should be t Treated at	aken 1 hour after Treated in doctor's	THU.	
GI diarrhea nausea vomiting mouth sores	s: DAC and TH or 2 h	ours after a meal	DAC should be t Treated at	aken 1 hour after Treated in doctor's	THU.	
GI diarrhea nausea vomiting mouth sores neuropathy	or 2 h	ours after a meal	DAC should be t Treated at	aken 1 hour after Treated in doctor's	THU.	
GI diarrhea nausea vomiting mouth sores neuropathy tingling hands an	or 2 h	ours after a meal	DAC should be t Treated at	aken 1 hour after Treated in doctor's	THU.	
GI diarrhea nausea vomiting mouth sores neuropathy tingling hands an sensitivity to colo	or 2 h	ours after a meal	DAC should be t Treated at	aken 1 hour after Treated in doctor's	THU.	
GI diarrhea nausea vomiting mouth sores neuropathy tingling hands an sensitivity to colo general	or 2 h	ours after a meal	DAC should be t Treated at	aken 1 hour after Treated in doctor's	THU.	
GI diarrhea nausea vomiting mouth sores neuropathy tingling hands an sensitivity to colo general Fever	or 2 h	ours after a meal	DAC should be t Treated at	aken 1 hour after Treated in doctor's	THU.	
GI diarrhea nausea vomiting mouth sores neuropathy tingling hands an sensitivity to colo general Fever Infection	or 2 h	ours after a meal	DAC should be t Treated at	aken 1 hour after Treated in doctor's	THU.	
GI diarrhea nausea vomiting mouth sores neuropathy tingling hands an sensitivity to colo general Fever Infection swelling arms/leg	or 2 h	ours after a meal	DAC should be t Treated at	aken 1 hour after Treated in doctor's	THU.	
GI diarrhea nausea vomiting mouth sores neuropathy tingling hands an sensitivity to colo general Fever Infection swelling arms/leg fatigue	or 2 h	ours after a meal	DAC should be t Treated at	aken 1 hour after Treated in doctor's	THU.	
GI diarrhea nausea vomiting mouth sores neuropathy tingling hands an sensitivity to colo general Fever Infection swelling arms/leg fatigue Injection site	or 2 h	ours after a meal	DAC should be t Treated at	aken 1 hour after Treated in doctor's	THU.	
GI diarrhea nausea vomiting mouth sores neuropathy tingling hands an sensitivity to colo general Fever Infection swelling arms/leg fatigue Injection site redness/swelling	or 2 h	ours after a meal	DAC should be t Treated at	aken 1 hour after Treated in doctor's	THU.	
GI diarrhea nausea vomiting mouth sores neuropathy tingling hands an sensitivity to colo general Fever Infection swelling arms/leg fatigue Injection site	or 2 h	ours after a meal	DAC should be t Treated at	aken 1 hour after Treated in doctor's	THU.	

15.2.2 Appendix 2: Sample Medication Self-Administration Record and Patient Diary

swollen glands near injection			
near injection			
site			
rash			
Respiratory			
sore throat			
runny nose			
cough			
Other:			

15.2.3 Appendix 3: Study Calendar

Screening to Completion of DAC-THU/Pembrolizumab

				istered only	regression	Onwards]* ho exhibit stable disease	
Procedure	Screening Within 4 weeks prior to enrollment	Baseline Within 10 days prior to start of DAC- THU	During T Day 1 of DAC- THU	Treatment Day 2 of DAC- THU	Within 3 days prior to completion of DAC- THU	At the end of course completion	End of Treatment Visit ⁷
History and PE	Х	X				Х	Х
Vital signs	Х	X				Х	Х
Performance Score	Х	X				Х	
NCI LP Confirmation of Dx ¹	Х						
CBC with differential; Acute Care Panel, Hepatic Panel (Sections 2.2 and 3.4.1)	Х	Х			ng Course 1, ess clinically d	Х	Х
PT, PTT	Х	X			ng Course 1, ess clinically d	Х	
Thyroid Function Tests						Х	
Albumin, Ca ²⁺ total, Mg ²⁺ total, Phosphorus, LD, Total Protein, Total CK, Uric Acid		X			ng Course 1, ess clinically d	Х	Х
Fetal Hemoglobin		X					
Urinalysis		X4				X^4	
Anti HIV, anti HCV, HBsAg, anti-HAV IgM, and if needed, HCV RNA	Х						
Urine or serum HCG in women of childbearing potential	X ³	X ³					
T, B, NK cell subsets		X9				Х	

				stered only	I+1 [Course 2 for patients we regression	Onwards]* ho exhibit stable disease	
	Screening Within 4 weeks	Baseline Within 10 days prior to start of DAC-	Day 1 of DAC-	Treatment Day 2 of DAC-	Within 3 days prior to completion of DAC-	At the end of course completion	End of Treatment
Procedure	prior to enrollment	THU	THU	THU	THU		Visit ⁷
HLA class I and class II analysis of PBMC	\mathbf{X}^1						
EKG	Х						
Echocardiogram	Х						
PFTs	Х	X					
ABGs (to be drawn if pulse oximetry <90% on room air)	Х	X					
Lupus Anticoagulant and ANA	Х						
Radiological Assessments	\mathbf{X}^2					X^2	
DAC-THU			Once a d	ay on days dose lev	according to el		
Tumor sample for research ⁸		Х				Х	
Correlative Research Studies		X ⁵	X ⁵		X ⁵		
PK/PD			X6	X6			
Adverse Events ¹⁰			х —			→	
Concomitant Medications ¹⁰		X				→	

^{1.} May be obtained any time prior to initiation of study therapy. Does not need to be repeated if already done at NCI.

^{2.} Radiological Assessments: Pre-enrollment screening assessment: X-rays, contrast enhanced CT scans of chest, abdomen, pelvis, as well as brain MR (no gadolinium contrast), and fused PET-CT scans to evaluate the status of disease. (All imaging must be obtained within 4 weeks prior to treatment.) At the end of each course completion assessment: CT scan (C/A/P) (with standard oral/IV contrast), fused PET/CT scan and brain MR without gadolinium contrast (or CT scan if MR contraindicated).

³ Must be completed within 3 days prior to enrollment or 48 hours prior to start of study drugs.

^{4.} Urinalysis and culture if indicated.

- ^{5.} See Appendix 4 for details of Research Labs timepoints and collection details. Note: Tubes/media may be adjusted at the time of collection based upon materials available if approved by the PI/laboratory investigator.
- ^{6.} See Appendix 4 for PK sampling timepoints and collection details. Note: PK samples will only be drawn on Day 1 and Day 2 of Cycle 1.
- ^{7.} End of treatment visit will occur approximately 30 days after the last dose of study drug. If the patient cannot return to the Clinical Center for this visit, a request will be made to collect required clinical labs (specify as needed) from a local physician or laboratory. If this is not possible, patients may be assessed by telephone/or other NIH approved remote platforms for symptoms.
- ^{8.} Tumor biopsy will be performed at baseline if screening biopsy was not performed and after one course of therapy (Week 10 +/- one week).
- ⁹ Every three weeks during therapy.
- ^{10.} Adverse events and concomitant medications will be assessed weekly during the dose finding portion of the trial and every three weeks prior to the administration of pembrolizumab during the expansion portion of the trial.

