- 2.1.1.11 Patients must be without evidence of unstable or decompensated myocardial disease; and must have adequate pulmonary reserve evidenced by FEV1 and DLCO \geq 35% predicted; oxygen saturation equal to or greater than 90% on room air by pulse oximetry or ABG (to be drawn if pulse oximetry < 90% on room air).
- 2.1.1.12 No immunosuppressive medications except non-systemic corticosteroids.

2.1.1.13 Patients must have normal organ and marrow function as defined below:

– leukocytes	\geq 3,000/mcL
– absolute neutrophil count	\geq 1,500/mcL (without transfusion or cytokine
	support)
 absolute lymphocyte count 	> 800/mcL
– absolute lymphocyte count – platelets	$\geq 100,000/mcL$
– PT	no more than 2 seconds above the ULN
– total bilirubin	< 1.5 X institutional upper limit of normal
	OR
 direct bilirubin 	\leq ULN for patients with total bilirubin > 1.5
	ULN
– serum albumin	\geq 2.0 mg/dL
– AST(SGOT)/ALT(SGPT)	\leq 2.5 X institutional ULN
- creatinine	\leq 1.6 mg/ml
	OR
- creatinine clearance (eGFR)	$\geq 60 \text{ mL/min}/1.73 \text{ m}^2$ for patients with
	creatinine levels above institutional normal
	at the time DAC-THU and pembrolizumab
	treatment commences.
	d'admont commences.

- 2.1.1.14 Patients with history of brain metastases except those with meningeal carcinomatosis or leptomeningeal disease may be eligible for treatment a minimum of 1 week following completion of gamma knife or whole brain radiotherapy, or 4 weeks following surgical resection of brain metastasis provided post-treatment MR scan reveals no evidence of active disease, and no ongoing need for systemic steroids.
- 2.1.1.15 Patients with laboratory evidence of autoimmune disease (e.g., positive ANA or lupus anticoagulant) without associated symptoms; vitiligo, or mild autoimmunity not impacting the function of organs, such as Hashimoto or psoriasis may be eligible for study.

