3 STUDY IMPLEMENTATION

3.1 STUDY DESIGN

This trial is unique in that it is intended to establish the rationale and conditions for the use of oral DAC-THU and pembrolizumab therapy for NSCLC, EsC, and MPM. The goal is to establish the basis for subsequent evaluation of this treatment regimen in combination with other agents targeting MDSC, or adoptive immunotherapy regimens in patients with thoracic malignancies.

Patients potentially eligible for trial will be evaluated, and undergo subsequent eligibility assessment in the Thoracic Surgery Clinic/NCI. Patients meeting eligibility criteria will undergo baseline (if fresh tumor biopsy was not performed at screening) and post treatment tumor biopsies either by percutaneous image-guided FNA techniques in Interventional Radiology (Clinical Center/NIH) or endoscopic/thoracoscopic techniques in the CC operating room by Thoracic Surgery staff using standard of care practice guidelines. Tumor biopsies may be omitted at the discretion of the PI if risks outweigh potential research benefits.

The Phase I component will be a standard 3+3 design starting with oral DAC-THU on two consecutive days (preferably Tuesday and Wednesday) for two weeks out of three weeks for 9

weeks with incremental dose escalation as shown in Section **3.1.3**. Patients with high PD-L1 tumor expression will be combined with patients with low PD-L1 tumor expression to minimize accrual numbers required for the Phase I component of the study. Pembrolizumab will be administered on Wednesday, Thursday or Friday at a fixed intravenous dose of 200 mg q 3 weeks. One cycle is three weeks; one course is 9 weeks. Treatment evaluation including repeat tumor biopsy will be performed after one course of therapy (Week 10 +/- one week). Those patients exhibiting disease progression or unacceptable toxicities will be removed from study. Patients exhibiting stable disease or disease regression will be offered an additional course of therapy followed by treatment evaluation (without mandatory biopsy). Treatment will continue in this manner until off-study criteria have been met.

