3.3.6.2 Criteria to Resume Pembrolizumab Treatment

Subjects may resume treatment with study drug when the drug-related AE(s) resolve to Grade ≤ 1 or baseline value, with the following exceptions:

- Subjects may resume treatment in the presence of Grade 2 fatigue.
- Subjects who have not experienced a Grade 3 drug-related skin AE may resume treatment in the presence of Grade 2 skin toxicity.
- Subjects with baseline Grade 1 AST/ALT or total bilirubin who require dose delays for reasons other than a 2-grade shift in AST/ALT or total bilirubin may resume treatment in the presence of Grade 2 AST/ALT OR total bilirubin.
- Subjects with combined Grade 2 AST/ALT AND total bilirubin values meeting discontinuation parameters should have treatment permanently discontinued.
- Drug-related pulmonary toxicity, diarrhea, or colitis, must have resolved to baseline before treatment is resumed. Subjects with persistent Grade 1 pneumonitis after completion of a steroid taper over at least 1 month may be eligible for retreatment.
- Drug-related endocrinopathies adequately controlled with only physiologic hormone replacement may resume treatment.

If the criteria to resume treatment are met, the subject should restart treatment at the next scheduled time point per protocol. However, if the treatment is delayed past the next scheduled time point per protocol, the next scheduled time point will be delayed until dosing resumes.

If treatment is delayed or interrupted for > 6 weeks, the subject must be permanently discontinued from study therapy unless there is evidence (stable disease or disease regression) of clinical benefit.

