3.4 ON STUDY PROTOCOL EVALUATION (APPENDIX 3: STUDY CALENDAR)

3.4.1 Baseline Assessments

Note: Baseline assessments do not need to be repeated if performed during screening in the designated time frame.

Any Time Prior to Initiation of Treatment:

- a. HLA class I and class II analysis of PBMC.
- b. Tumor biopsy if fresh sample from previous biopsy is not available. Note: Samples collected on 06C0014 or any other NCI protocol in which the patient is co-enrolled can be used.

Within 10 Days Prior to Commencing DAC-THU/Pembrolizumab Therapy:

- a. Physical examination including assessment of vital signs and ECOG status.
- b. Chemistries
 - i. Acute Care Panel Sodium (Na), Potassium (K), Chloride (Cl), Total CO2 (bicarbonate), Creatinine, Glucose, Urea nitrogen (BUN),
 - ii. Mineral Panel Albumin, Calcium total, Magnesium total (Mg), Phosphorus
 - iii. Hepatic Panel Alkaline Phosphatase, ALT/GPT, AST/GOT, Total Bilirubin, Direct Bilirubin
 - iv. LD, Total Protein, Total CK, Uric Acid
- c. Fetal hemoglobin
- d. CBC, differential, platelet count, PT, PTT
- e. T, B, NK cell subsets
- f. Urinalysis and culture if indicated
- g. Pulmonary Function Test
- h. Arterial Blood Gas on room air (to be drawn if pulse oximetry <90% on room air).
- i. Research Labs (refer to Appendix 4 for details).

Within 48 Hours Prior to Initiation of DAC-THU/Pembrolizumab Therapy:

a. Women of child-bearing potential will have a urine or serum βhCG pregnancy test.

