3.4.2 Treatment Evaluation

Twice Weekly During First Course of Therapy, and Weekly Thereafter Unless Clinically Indicated:

- a. CBC with differential
- b. Sodium (Na), Potassium (K), Chloride (Cl), Total CO2 (bicarbonate), Creatinine, Glucose, Urea nitrogen (BUN), Albumin, Calcium total, Magnesium total (Mg), Phosphorus, Alkaline Phosphatase, ALT/GPT, AST/GOT, Total Bilirubin, Direct Bilirubin, LD, Total Protein, Total CK, Uric Acid
- c. PT/PTT

Note: The patient may have lab work obtained through his or her local physician.

Every Three Weeks During Therapy:

a. T, B, NK cell subsets

Performed After Each Course:

- a. Physical examination including assessment of vital signs and ECOG status.
- b. Sodium (Na), Potassium (K), Chloride (Cl), Total CO2 (bicarbonate), Creatinine, Glucose, Urea nitrogen (BUN), Albumin, Calcium total, Magnesium total (Mg), Phosphorus, Alkaline Phosphatase, ALT/GPT, AST/GOT, Total Bilirubin, Direct Bilirubin, LD, Total Protein, Total CK, Uric Acid
- c. CBC, differential, platelet count, PT, PTT
- d. Thyroid Function Tests
- e. T, B, NK cell subsets
- f. Urinalysis and culture if indicated
- g. Biopsy of index lesion (only on first treatment evaluation).

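### Thyroid function is first scheduled at about week 10, with no baseline and no End of Treatment value, so pre-existing and treatment-emergent thyroid abnormalities cannot be reliably told apart

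*Combined protocol and SAP*

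**What the plan says.** Thyroid testing is scheduled in two places, and they agree. Section 3.4.2 lists "d. Thyroid Function Tests" under the heading "Performed After Each Course". The study calendar in Appendix 3 has a row "Thyroid Function Tests" with a single mark, in the column for the end of course completion.

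The test appears in none of the other scheduled lists:

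- Section 2.2 (screening): blood counts, acute care and hepatic panels, clotting, viral markers, lupus anticoagulant and ANA.
- Section 3.4.1 (within 10 days before treatment): the chemistries end with "LD, Total Protein, Total CK, Uric Acid"; the rest of the list has no thyroid test.
- Section 3.4.2 (twice-weekly or weekly labs within a course).
- Section 3.4.4 (follow-up toxicity labs).
- Appendix 3, Screening, Baseline and End of Treatment columns.

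On timing, Section 3.1 gives pembrolizumab "at a fixed intravenous dose of 200 mg q 3 weeks" and states "One cycle is three weeks; one course is 9 weeks", with evaluation at week 10 plus or minus one week.

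On who may enter, criterion 2.1.1.15 says that patients with "mild autoimmunity not impacting the function of organs, such as Hashimoto or psoriasis may be eligible for study". Criterion 2.1.1.2 admits NSCLC patients whose first-line treatment included a checkpoint inhibitor.

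**The concern.** Toxicity is a Phase I primary objective (Section 1.1.1), and thyroid disturbance is a common immune-mediated effect of pembrolizumab in the protocol's own background table. When an abnormal value first appears at about week 10, the investigator must judge whether treatment caused it, with no earlier protocol value to compare. The error can go either way: an old abnormality may be counted as drug-related, or a new one put down to prior disease.

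A patient who stops during Course 1 and attends the 30-day visit passes through the trial with no scheduled thyroid value. What is at stake is how accurate and complete the thyroid entries in the toxicity tables are.

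**Working it through.** No sample size, power or alpha figure is involved. The check sets the schedule against the rules that use its results.

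**1. Doses before the first test.** Course length / dosing interval = 9 weeks / 3 weeks = 3 pembrolizumab doses. The evaluation in Section 3.1.1 is on Days 64 and 65, plus or minus 7 days.

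**2. Could the missing marks come from a damaged table?** No. The prose of Section 3.4.2 places the test only after each course, and the prose lists in Sections 2.2, 3.4.1 and 3.4.4 omit it. The calendar matches the text.

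**3. Who could arrive with an abnormal value?** Hashimoto patients under 2.1.1.15, checkpoint-pretreated NSCLC patients under 2.1.1.2, and anyone with undiagnosed or subclinical disease.

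**4. What depends on attribution?** Section 6.1.2.1 keeps all Grade 1 events, and Grade 2 events not related to treatment, in source documents only. A Grade 2 thyroid event therefore enters the database only if judged related. This is the grade range that matters: in the cited phase III first-line trial (table in Section 1.2.10, 154 pembrolizumab patients) every thyroid event was below Grade 3.

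| Event | Any grade | Grade 3–5 | Rate |
|---|---|---|---|
| Hypothyroidism | 14 | 0 | 14/154 = 9.1% |
| Hyperthyroidism | 12 | 0 | 12/154 = 7.8% |
| Thyroiditis | 4 | 0 | 4/154 = 2.6% |

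The first two are the most frequent immune-mediated events in that table.

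**5. Scale, if those rates carried over.**

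- 78 evaluable patients: 78 × 14/154 = 7.1 hypothyroid; 78 × 12/154 = 6.1 hyperthyroid.
- 85 patients (accrual ceiling): 85 × 14/154 = 7.7; 85 × 12/154 = 6.6.

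The two groups may overlap. These are expected events over that trial's follow-up, not counts of errors.

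**6. Early leavers.** Section 6.3.2 makes all patients evaluable for toxicity from first treatment. Those who progress after 3 weeks but before completing 9 are taken off treatment and are evaluable for toxicity only. They leave before the only scheduled test, and neither the Section 3.4.4 labs nor the End of Treatment column supplies one. A patient who leaves partway through a later course has earlier end-of-course values but none scheduled after the last doses.

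**The case against.** The strongest reply is that prose and calendar agree, so this is a deliberate schedule, and that other safeguards cover most of the gap. Much of that stands:

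- Medical history and examination are required at screening, and routine baseline medications are captured (Section 6.1.2.2), so known or treated thyroid disease would be visible. Criterion 2.1.2.9 also excludes a history of thyroiditis, although it sits beside the Hashimoto allowance and no scheduled test would find unrecognised disease.
- Investigators must judge relationship and give an alternate cause for unrelated events (Section 8.2).
- The endocrine table in Section 3.3.6.1 foresees FT4 and TSH work-up when an endocrinopathy is suspected, and adverse events are assessed regularly. Early leavers are therefore not scheduled for a test; it does not follow that they are never tested.

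A reader might infer three stronger consequences, which the documents do not support:

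- *The resumption rule cannot work without a baseline.* Section 3.3.6.2 begins "Subjects may resume treatment with study drug when the drug-related AE(s) resolve to Grade" 1 or below, or to the baseline value. Grade 1 or below is enough, and the section has a separate exception for endocrinopathies controlled on physiologic replacement. The endocrine table does not use a baseline thyroid value either.
- *Dose-limiting toxicity or the MTD is distorted because the first test falls after the 6-week window.* A DLT needs Grade 3 or worse, or toxicity that ends treatment (Section 3.1.2). The cited trial had no thyroid event of Grade 3 or worse, and the endocrine table continues pembrolizumab at Grades 1 and 2. Any effect is negligible on these figures.
- *A definite number of patients would be misattributed.* Assuming that 3% to 10% have an abnormal value at entry (not given in the documents), 85 × 0.03 = 2.6 and 85 × 0.10 = 8.5. Reading this as misattributed events requires all 85 to be tested, and every abnormality to be both recorded and blamed on the drug. Sections 6.1.2.1 and 8.2 contradict that.

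**Conclusion.** The gap is real but limited. The plan as written never collects a thyroid reference value and schedules none at the end of treatment. This weakens attribution for undiagnosed or subclinical disease, for enrolled Hashimoto patients and for checkpoint-pretreated patients, and leaves those who stop within Course 1 with no scheduled value.

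The scale of the toxicity concerned is about 7 to 8 hypothyroid and 6 to 7 hyperthyroid events in 78 to 85 patients, assuming the pembrolizumab-alone rates apply to this combination. Those rates come from a trial with median progression-free survival of 10.3 months, so they do not size what is missed in someone who leaves at week 5. The documents do not give the number misclassified or missed, or the direction of the net error.

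The response endpoint, sample size and error rates are untouched. This is an inexpensive improvement to the safety data; the schedule does not contradict itself.

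**What to change.** 1. Add thyroid function tests to the Section 3.4.1 list of assessments within 10 days before treatment.
2. Mark them under Baseline and End of Treatment in Appendix 3.
3. Add them to the toxicity laboratory list in Section 3.4.4.
4. State in Section 10.1 that thyroid toxicity will be reported relative to baseline, and give the number of patients with both a baseline and a later value.

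The cost is one more assay at each of two visits where blood is already scheduled. The End of Treatment value will not always be available: footnote 7 of Appendix 3 allows local laboratory collection or, failing that, a telephone or remote assessment, so the test may have to be done locally or may be missed. The change concerns data collection only and alters no dose, hold or resumption rule.
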